6.2.4 PREPARATION

Not applicable

6.3 MEASURES TO MINIMIZE BIAS: RANDOMIZATION AND BLINDING

Participants will be blinded to the stimulation changes in Phase II, conditions (1) & (2) as described in the study design. Any blinded ratings of the MDS-UPDRS Part III will be done at the discretion of the PI.

6.4 STUDY INTERVENTION COMPLIANCE

Adherence to the protocol will be assessed via completed study tasks during each of the study phases and conditions.

6.5 CONCOMITANT THERAPY

For this protocol, a prescription medication is defined as a medication that can be prescribed only by a properly authorized/licensed clinician. If a subject is not taking carbidopa/levodopa 25/100 as part of their routine treatment, the principal investigator will prescribe the number of tablets needed for Phase I and II. Subject's dopaminergic medications will be withdrawn the night before each study visit, but they will remain on all other prescription medications. A drug-drug interaction is not anticipated during the study visit with carbidopa/levodopa, as PD subjects, especially those with gait disorder, remain on some formulation of levodopa.

6.5.1 RESCUE MEDICINE

Not Applicable

7 STUDY INTERVENTION DISCONTINUATION AND PARTICIPANT DISCONTINUATION/WITHDRAWAL

7.1 DISCONTINUATION OF STUDY INTERVENTION

This study does not require continuous follow-up. All assessments and interventions will be conducted during the study visits and subjects will return to their default DBS settings and medication regimen after each visit. There will be no change to their standard of care PD management.

If a subject is unable to complete the study visit due to occurrence of any of the aforementioned potential risks, they will be offered the opportunity to complete the remainder of the study at another study visit within 4 weeks.

The data to be collected at the time of study intervention discontinuation will include the following:

- Any demographic and clinical data
- Sensor based data

7.2 PARTICIPANT DISCONTINUATION/WITHDRAWAL FROM THE STUDY

Participants are free to withdraw from participation in the study at any time upon request.

An investigator may discontinue or withdraw a participant from the study for the following reasons:

- Significant study intervention non-compliance
- If any clinical adverse event (AE) or other medical condition or situation occurs such that continued participation in the study would not be in the best interest of the participant

- Disease progression which requires discontinuation of the study intervention
- If the participant meets an exclusion criterion (either newly developed or not previously recognized) that precludes further study participation

The reason for participant discontinuation or withdrawal from the study will be recorded on the Case Report Form (eCRF). Subjects who sign the informed consent form, and receive the study intervention, and subsequently withdraw, or are withdrawn or discontinued from the study, will be replaced.

7.3 LOST TO FOLLOW-UP

A participant will be considered lost to follow-up if he or she fails to return for 2 scheduled visits if they are undergoing DBS implantation or at most 2 study visits if they are considered chronic DBS subjects and is unable to be contacted by the study site staff.

The following actions must be taken if a participant fails to return to the clinic for a required study visit:

- The site will attempt to contact the participant and reschedule the missed visit within 4 weeks and counsel the participant on the importance of maintaining the assigned visit schedule and ascertain if the participant wishes to and/or should continue in the study.
- Before a participant is deemed lost to follow-up, the investigator or designee will make every effort to regain contact with the participant (where possible, 3 telephone calls and, if necessary, a certified letter to the participant's last known mailing address or local equivalent methods). These contact attempts should be documented in the participant's medical record or study file.
- Should the participant continue to be unreachable, he or she will be considered to have withdrawn from the study with a primary reason of lost to follow-up.]

8 STUDY ASSESSMENTS AND PROCEDURES

8.1 EFFICACY ASSESSMENTS

Description of the Study Phases. This study will be conducted in two phases: **Phase I**. Each subject will then be evaluated during an in-laboratory session under two conditions: 1) the practically defined OFF state following overnight withdrawal of their dopaminergic medications; and 2) levodopa ON State. Participants will be given 1.5 times their usual levodopa dose (up to 300mg) to ensure transition to the ON state in-laboratory, and experimenters will repeat assessments 1 hour afterwards (or sooner based on patient report and visual confirmation by physician). Cognitive function in the ON state will be captured via the Mini Mental Status Exam (MMSE) by a study coordinator or physician. Phase I for preoperative subjects will be integrated into their standard of care core assessment program for surgical interventional therapies in Parkinson's disease (CAPSIT-PD) (42). For those subjects with chronic DBS, their stimulators will be turned off for at least 50 minutes to ensure adequate "wash-out" of stimulation effects (43) prior to the assessment in each condition. If symptoms become intolerable, the wash out period may be shortened. This will be determined by the PI on a case by case basis.

During each condition, a movement disorder's specialist will conduct an assessment of items 3.1, 3.3(a-e), 3.9, 3.11, 3.12, 3.13 of MDS-UPDRS III. Afterwards, each participant will be outfitted with full body Opal sensors (APDM, Opal, and Portland, OR) affixed to the wrists, feet, sternum and lumbar spine (L5 level). A trained research coordinator will instruct each participant to conduct the Stand and Walk (SAW)

test. During this test, subjects will stand for 30 seconds quietly, then walk 7 meters at their comfortable speed, turn 180 degrees, and walk back. Walking aides will be permissible, if needed. Unless the participant is unable to do so, the SAW test will be conducted twice for each trial in order to capture a sufficient number of gait cycles. Based on normative spatial-temporal gait analysis in healthy young and elderly adults (44-46), we selected the following measurements to be assessed during this instrumented walk: 1) Postural sway – root mean square (RMS) sway in antero-posterior (AP) and medio-lateral (ML) planes; 2) Gait – cycle duration (seconds), speed (m/s), stance (%), swing (%), heel strike angle (degrees), toe off angle (degrees), stride length (cm), cadence (steps/min), step duration (seconds), elevation at midswing (cm) (foot clearance), double support (%), arm swing velocity (deg/s), and range of motion (degrees); 3) Circumduction – turn angle (degrees), turn duration (seconds), and turn velocity (deg/s).

Following the gait testing, participants will undergo tremor and bradykinesia analysis with the Kinesia inertial sensors (Great Lakes Technologies, OH) that will be affixed to their finger and ankle. While seated, subjects will be guided through a series of movement tasks by interacting with the ONE tablet from Kinesia. Each motor test will appear on the touch screen interface that will instruct the participant on the motor task. The following tasks will be performed to assess bradykinesia: finger taps, hand grasps, wrist rotation, toe taps and leg lifts. The tremor assessments will be determined from the following tasks: arms resting (resting tremor), arms extended (postural tremor), and finger to nose (action tremor). Each motor task will last 15 seconds.

Phase II. Participants will be evaluated in two conditions: 1) OFF medication/ON stimulation; 2) ON medication/ON stimulation.

During condition (1), patients will be evaluated following overnight withdrawal of dopaminergic medications. Afterwards, each electrode contact will be reprogrammed by the Lead Principal Investigator in both low frequency and HFS. For each of the 4 contacts on both electrodes, the amplitude will be slowly increased by 0.1-V increment until sustained sensory or motor side effects are produced in HFS. The amplitude below the side effect threshold will be used along with a standard pulse width of 60 μ s. For low frequency stimulation (LFS) programming, milliamps will be adjusted to keep the total electrical energy delivered (TEED) between both LFS and HFS conditions equivalent for each respective contact. The TEED is calculated as milliamp² x frequency x pulse width/impedance (47).

The opal body sensors (APDM, Opal, Portland, OR) will be fixed to each subject's wrists, ankles, sternum and lumbar spine and the SAW task will be carried out by the research coordinator for each combination of low and high frequency stimulation for the four contact pairs (total of 8 trials with each contact pair being either LFS or HFS, exclusively; refer to Figure 1). The gait measurements will be the same as in Phase I. Bradykinesia and tremor assessments will be conducted for each combination of stimulation and contact pairs using the Kinesia inertial sensors (Great Lakes Technologies, OH) as well. To minimize participant fatigue, the following bradykinesia and tremor assessments will be conducted during this phase: Hand grasps, leg lifts, rest tremor and postural tremor. Ratings of items 3.1, 3.3 (a-e), 3.9, 3.11, 3.12, 3.13 of MDS-UPDRS III will also be conducted for each stimulation contact pairing. Following each stimulation parameter change, there will be a 10-minute latency before the gait task is conducted. The participants will be blinded to each stimulation change.

During condition (2), the stimulators will be turned off and subjects will be given 1.5 times their usual levodopa dose (up to 300mg) to ensure transition to the medication ON state. Retesting will be done 1 hour after the levodopa challenge (or sooner based on patient report and visual confirmation by physician). Gait, bradykinesia and tremor sensor assessments as well as MDS-UPDRS III rigidity and axial

subscore ratings will be conducted in the same manner as condition (1). The participants will be blinded to stimulation changes. At the completion of Visit 2, participants will return to their initial programming settings and resume their medication regimen as per their standard of care. If participant fatigue develops, he/she will have the option to complete condition (2) on another visit within a 4 week time period.

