2.3 RISK/BENEFIT ASSESSMENT

2.3.1 KNOWN POTENTIAL RISKS

Patients will be withdrawn from their PD medications the night before the study visit(s) in order to be assessed in practically defined OFF state. Subjects will experience more of their parkinsonian motor symptoms including possible worsening of their gait which could increase their risk of falling.

When carbidopa/levodopa 25-100 tablet(s) are administered orally, subjects may experience lightheadedness, nausea, hypotension, and/or fatigue.

During the DBS adjustments, transient stimulation induced sensory (e.g., paresthesia) or motor symptoms (e.g. muscle contractions or pulling sensations) may occur as amplitudes are incrementally raised for each electrode contact during Phase II.

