2.3.3 ASSESSMENT OF POTENTIAL RISKS AND BENEFITS

Potential Benefits:

Expected Outcomes: Aim 1. We would have extensively investigated the impact of 60Hz stimulation on several gait spatiotemporal domains (e.g., pace, turning, postural sway) and relate it to other stimulation features (e.g., activated electrode contacts, therapeutic amplitudes) using wearable sensors. We will also determine the influence that levodopa has on 60Hz stimulation in the context of kinematic gait changes. These results can help facilitate the application of this stimulation to certain PD-DBS subpopulations. Aim 2. Our results will allow for instantaneous recommendations by artificial intelligence on which stimulation frequency is best suitable for a subject based on *a priori* sensor measurements of motor symptoms. The ranking provided can guide clinical evaluations and potentially reduce the amount of time needed for programming by changing the “trial and error” paradigm to a sensor guided paradigm with either 60Hz or HFS initiated from the outset.

Potential Risks:

Subjects will be closely monitored following administration of carbidopa/levodopa 25/100mg tablet(s) to ensure any side effects are minimized and addressed immediately.

Any stimulation side effect will immediately be alleviated with reduction in DBS amplitude. All assessments will be done at amplitudes below the side effect threshold. Furthermore, all sensor assessments will be conducted in a control setting with the research coordinator and Principal investigator present at all times to minimize risk any risk of falling during the gait assessment.

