Phase II. The primary goal of Phase II is to investigate the impact of stimulation frequencies (low and high), stimulation spatial characteristics and levodopa on gait kinematic domains. Participants will be evaluated in two conditions: 1) OFF medication/ON stimulation; 2) ON medication/ON stimulation. Patient's weight will be collected prior to this assessment. For chronic DBS patients, phase II will commence during study visit 1. For preoperative subjects, phase II will be conducted on a separate visit (study visit #2) that will take place 12-15 weeks after initial programming of bilateral STN deep brain stimulation implantation. This visit will also be conducted in a laboratory setting. The impact of the lesion effect from the surgery would also be avoided with this timeframe.

During condition (1), patients will be evaluated following overnight withdrawal of dopaminergic medications. Afterwards, each electrode contact will be reprogrammed by the Lead Principal Investigator in both low frequency and HFS. For each of the 4 contacts on both electrodes, the amplitude will be slowly increased by 0.1-V increment until sustained sensory or motor side effects are produced in HFS. The amplitude below the side effect threshold will be used along with a standard pulse width of 60 μ s. For low frequency stimulation (LFS) programming, milliamps will be adjusted to keep the

total electrical energy delivered (TEED) between both LFS and HFS conditions equivalent for each respective contact. The TEED is calculated as milliamp² x frequency x pulse width/impedance (47).

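### Matching energy at 60 Hz requires 1.47 to 1.76 times the HFS amplitude, yet the side-effect threshold is measured only in HFS and all testing is said to stay below it; the plan does not reconcile these rules

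*Combined protocol and SAP*

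**What the plan says.** Sections 4.1 and 8.1 describe the same Phase II programming. For each contact, amplitude is raised in steps of 0.1 "until sustained sensory or motor side effects are produced in HFS". An amplitude below that threshold is then used with a 60 µs pulse width. For 60 Hz, "milliamps will be adjusted to keep the total electrical energy delivered (TEED) between both LFS and HFS conditions equivalent for each respective contact", and both sections give the formula: "The TEED is calculated as milliamp² x frequency x pulse width/impedance".

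Section 2.3.3 gives two assurances: "All assessments will be done at amplitudes below the side effect threshold", and "Any stimulation side effect will immediately be alleviated with reduction in DBS amplitude". It names no frequency.

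Section 1.3 speaks of a single side-effect threshold found at the contact evaluation. For chronic DBS patients evaluated at a clinical visit, it relies on that threshold for up to six months. Sections 6.1.1 and 6.1.2 cover programming at both frequencies but leave out the energy-matching step. No section describes a threshold search at 60 Hz, a limit on the 60 Hz amplitude, or which rule gives way if the two meet.

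Section 9.4.2 (Aim 1.1) compares high and low frequency over all contact pairs in the levodopa-OFF state.

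**The concern.** TEED rises with frequency and with the square of amplitude. Lowering the frequency to 60 Hz while holding TEED constant therefore pushes amplitude up. The starting point is an HFS amplitude set by reference to the HFS threshold, so the matched 60 Hz amplitude can pass the only threshold that has been measured. The matching rule and the assurance in section 2.3.3 then point in different directions.

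Two things are at stake. One is a stated safety assurance that the programming steps do not visibly support. The other is the meaning of the primary contrast. If the 60 Hz amplitude is kept down, or reduced after a side effect, while HFS stays as it was, the match is lost for that contact. The 60 Hz trial then differs from its HFS counterpart in energy as well as frequency. The model described in section 9.4.2 has no amplitude or energy term. That is reasonable while the match holds, but it means the model cannot separate the two influences when the match fails.

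**Working it through.** **Inputs.** Low frequency: 60 Hz. HFS: 130-185 Hz (sections 2.1, 2.2 and 4.2) or 130-180 Hz (section 9.1). Pulse width: 60 µs, taken to apply at both frequencies because only milliamps are said to be adjusted. Impedance: taken as equal at both settings of a contact. The plan states no amplitude ratio, so there is no figure of its own to reproduce.

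**Step 1: required amplitude ratio.** Write A_L and A_H for the 60 Hz and HFS amplitudes and f_H for the high frequency. Equal TEED means A_L² × 60 = A_H² × f_H, because pulse width and impedance cancel. So A_L/A_H = √(f_H/60):
- 130 Hz: √(130/60) = 1.472
- 180 Hz: √(180/60) = 1.732
- 185 Hz: √(185/60) = 1.756

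**Step 2: when both rules can hold against the HFS threshold T.** Let m = A_H/T. A_L stays at or below T only if m ≤ 1/ratio: 1/1.472 = 0.679, 1/1.732 = 0.577, 1/1.756 = 0.569.

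**Step 3: size over assumed margins.** The plan says only that HFS is below T, so m is an assumption. The matched 60 Hz amplitude as a multiple of T is m × ratio:

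| m (assumed) | 130 Hz | 180 Hz | 185 Hz |
|---|---|---|---|
| 0.9 | 1.325 | 1.559 | 1.580 |
| 0.7 | 1.030 | 1.212 | 1.229 |
| 0.5 | 0.736 | 0.866 | 0.878 |

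If HFS is set one 0.1 step below an assumed threshold of 3.0 (so 2.9), the matched 60 Hz amplitude is 2.9 × 1.472 = 4.27 at 130 Hz and 2.9 × 1.756 = 5.09 at 185 Hz. These are 1.42 and 1.70 times the threshold.

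**Step 4: energy gap if the 60 Hz amplitude is held at T instead.** TEED_L/TEED_H = min(1, (60/f_H)/m²). The rule says below T, so these are upper limits:

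| m (assumed) | 130 Hz | 180 Hz | 185 Hz |
|---|---|---|---|
| 0.9 | 0.570 | 0.412 | 0.400 |
| 0.7 | 0.942 | 0.680 | 0.662 |
| 0.5 | 1 | 1 | 1 |

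**Step 5: the printed formula.** Current² × frequency × pulse width / impedance has units A² × s⁻¹ × s / Ω = A²/Ω, which is neither energy nor power. Current² × impedance, or voltage² / impedance, each times frequency and pulse width, gives watts, that is, energy per second. Impedance cancels in step 1 under any of these forms, so the ratios do not depend on which is used.

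**The case against.** The conflict is conditional. Section 2.3.3 does not say that its threshold is the HFS one, and sections 4.1, 6.1.1 and 8.1 say each contact is reprogrammed at both frequencies. If a separate and sufficiently high 60 Hz threshold is meant, both rules can hold. That is fair, and it limits the finding to rules that do not fit together as written. But no 60 Hz threshold search is described, and section 1.3 refers to one threshold only.

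It can also be said that equal TEED is stated expressly in the design and procedures sections, whereas section 2.3.3 is a general risk statement. That stands: equal energy is the planned contrast. What is missing is what happens when the general assurance, or the reduction of amplitude after a side effect, takes precedence for a given contact.

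A reader might infer that the formula error distorts the settings or the analysis. The documents do not support this. TEED is used only for matching within a contact, where the error cancels at unchanged impedance. No section plans to report TEED or to compare it across contacts or patients.

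A reader might also infer that delivered settings go unrecorded, since section 10.1.3 names only baseline DBS parameters. The data list in section 10.1.9.1 is not exhaustive and the case report form is not among the documents, so this cannot be concluded.

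**Conclusion.** The concern holds as an unreconciled conflict between the matching rule and the below-threshold assurance, and it should be fixed. Followed as written, matching needs a 60 Hz amplitude 1.47 to 1.76 times the HFS amplitude. This exceeds the measured threshold unless HFS is at or below about 57% to 68% of it, depending on the high frequency used. If the assurance prevails and HFS is at 90% of threshold (assumed), 60 Hz would deliver at most 57% of the HFS energy at 130 Hz and 41% at 180 Hz; with HFS at 50% of threshold there would be no gap.

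The ratios rest on equal pulse width and impedance at the two frequencies. The margins are assumptions because the plan gives none. It would go too far to read this as a prediction of side effects, unblinding or a safety breach at 60 Hz: tolerance at 60 Hz may differ from tolerance in HFS, and the documents contain no data on it. The formula and the frequency range are editorial matters.

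**What to change.** The sponsor should reconcile sections 2.3.3, 4.1, 6.1.1, 6.1.2 and 8.1 on four points:
- which threshold governs the 60 Hz setting;
- how that threshold fits with TEED matching;
- what happens to the match if amplitude is reduced;
- which amplitude unit applies. The titration step is in volts in sections 4.1, 6.1.1 and 8.1 and in V/mA in section 6.1.2, while the 60 Hz adjustment is in milliamps.

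No amplitude or clinical rule is proposed here.

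If not already captured, record for each trial the delivered amplitude with its unit, the impedance, and whether the TEED match was achieved. Report the number of unmatched trials. Keep the all-trials comparison as primary. Any analysis by match status should be labelled supportive, because it conditions on something that happens after the setting is applied and can be biased.

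Editorial: check and correct the TEED formula in sections 4.1 and 8.1, correct the HFS range printed as 130-85 Hz in the synopsis, and state one HFS range throughout.

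The cost is protocol wording, a few fields known at the time of programming, and a small amount of extra reporting.

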8.2 SAFETY AND OTHER ASSESSMENTS

Description of Consent and Procedure for Obtaining Informed Consent

Participants will be consented by the Lead Principal Investigator in person at the Parkinson's and Movement Disorders Center. All potential participants will be asked to review a copy of the informed consent form, regardless of diagnosis, unless there is evidence of serious mental disability that would impair judgment or reasoning. Patients will not be approached regarding study participation by anyone not directly involved in their treatment, unless the patient has given permission for this interaction or has self-referred. The patient will then be contacted by the Principal Investigator and will be offered written information about the study. Informed written consent will be obtained prior to any study assessment. Subsequent clinical evaluation may result in an exclusion from the study. The PI and research coordinator will review the informed consent form with potential participants and address any questions or concerns prior to obtaining written informed consent for participation. The research members will also address any future questions or concerns of participants. A copy of the consent will be provided to the participant after it has been signed and witnessed.

Remote consent will be employed during the COVID-19 pandemic through a combination of telephone and email contact by the investigator and coordinator per Northwell HRPP Policies and Procedures. Initial and/or interim discussions with the PI may also take place in-person during clinical visits. The coordinator will provide potential participants with a brief summary of the study and a copy of the consent document for review. If the subject is interested in participation, the PI will discuss the study and answer any questions. If the subject agrees to participate in research, he/she will be directed by the PI to sign the consent form and return it by mail or email (scanned consent form as a PDF) to the study coordinator. Alternative methods such as facsimile will be utilized depending on the subject's access. An enrollment note will be generated for each subject to document this process. Once the signed consent document is received by the coordinator, it will be forwarded to the PI for signature. The study team will note the date discrepancies of the signatures on both the consent document and enrollment note. The study coordinator will send a copy of the fully signed consent document to the subject for his/her files. When in-person consent is possible (e.g., during a clinical visit), traditional consent methods will be employed.

Study Visit 1 will be scheduled within 30 days of subject consent.

All study visits will be conducted by the PI and research coordinator in a controlled setting. Each subject will be closely monitored during each motor assessment to reduce risk of falls and will be queried regularly during the visit to assess for fatigue.

